Specific Aim #2 is to conduct a non-inferiority trial that compares the effectiveness of MB delivered by (a) mental health clinicians versus (b) paraprofessional home visitors.

Specific Aim #3 is to evaluate whether effectiveness of the two versions of MB (clinician led vs. paraprofessional home visitor led) varies according to patient characteristics (e.g., race, ethnicity, first-time mother, and/or geographic type of home visiting (HV) program (i.e., urban vs. rural).

Specific Aim #4 is to examine the feasibility and acceptability of MB delivered by paraprofessional home visitors and mental health clinicians.

Study time points include: baseline, immediately following the intervention period (or roughly eight weeks post enrollment for controls), 12 weeks postpartum, and 24 weeks postpartum. Primary time point of interest will be 24 weeks postpartum. This analysis plan will focus on the primary results manuscript, and thus, we will focus on Aims #1-#3.

Study Outcomes

Primary Outcome

Primary outcome of interest for Aims #1-#3 will be the Quick Inventory of Depressive Symptoms (QIDS-SR16) score as determined by participant self-report at 24 weeks postpartum. We will control for baseline QIDS-SR16 score. This is a continuous measure ranging from zero to 27 points, where higher scores signify increased depressive symptoms. QIDS-SR16 translates into depressive categories such that a score of less than five points indicates no depression, a score ranging from six to 10 indicates mild depression, 11-15 signifies moderate depression, 16-20

indicates severe depression, and anything above 20 would be labeled as very severe (<http://www.ids-qids.org/>). As a result, we deem a five-unit change or difference in score to be meaningful (as a jump in five points would result in an increase in depression severity tier for any individual patient).

Secondary Outcomes

The following secondary outcomes will further be examined in order to address subcomponents of specific aims and also to address some of the exploratory aims. These secondary outcomes align with key components of the Mothers and Babies intervention.

1. Incidence of major/clinical depression (major depressive episode [MDE])
 - a. A major depressive episode will be defined via the Maternal Mood Screener
 - b. MDE for the purposes of this study is defined as:
 - i. The participant indicates at least **five** of the problems listed within the past two weeks (part B on the form), **and**

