 - ii. **At least one** of the problems must be: symptom 1 (feeling depressed) or symptom 2 (losing interest or pleasure), **and**
 - iii. The participant indicates '**yes**' to the question: *Did these problems interfere with your life or activities a lot?*
2. Behavioral activation scale score (BA)
3. Social support (due to the highly skewed nature of this outcome, we dichotomized it into ≥ 4 versus <4).
4. Mood regulation
5. Decentering
6. Mental health service utilization (i.e., an indicator for whether participants are enrolled in therapy with a counselor and/or currently taking antidepressants). This outcome may be explored in greater detail in a separate paper; however, we plan to examine the difference between arms controlling for baseline mental health service utilization.

Tertiary Outcomes (the following will be explored in a separate paper from the primary results)

1. Pleasant activities
2. Perceived stress
3. Parental cognitions and conduct toward the infant scale
4. Dyadic adjustment scale
5. Flourishing scale
6. Prenatal health behaviors

The outcomes above are tied to validated scales with specific scoring requirements. The scoring instructions will be followed and analyses will proceed on the final, scored variables. In addition, we plan to summarize '**dosage**' of intervention in the active intervention arms as the number of sessions attended (out of six possible). We will also summarize the number of participants that were '**compliant**', which is defined as attending **at least four of the six sessions**.

Demographics and Baseline Assessments

The following are specific demographic/baseline assessments of interest for analyses. Primary analyses will adjust for these covariates as we anticipate they will influence outcome. We plan to report both adjusted and unadjusted intervention effect estimates:

1. Race/ethnicity (at the participant level): minority vs. not belonging to a minority category.
2. Whether participant is a first-time mother (i.e., current number of children = 0 at baseline).
3. Currently at risk for depressive episode (i.e., those NOT meeting criteria for MDE at baseline).

4. Primary language of intervention receipt (for MH and HV arms) or primary language in which the participant completed assessments (for control arm).
5. Education: at least some college vs. less than college.

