Analyses will be conducted on the modified intent-to-treat (mITT) dataset whereby all participants randomized with data at the 24-week time point will be analyzed according to arm to which they were allocated. We will further perform a sensitivity analysis on the 'as treated' dataset. Those in either active intervention arm will be considered 'treated' if they attend at least four out of the six sessions required for the Mothers and Babies course. For participants with missing data at baseline and non-missing data at follow-up, we plan to impute mean baseline values from the participants' follow-up in order to allow for inclusion in analyses.

Power and sample size considerations allowed for some missing data and, as specified in our approved research plan, we have allowed for up to two clusters to drop out of each arm; however, in the event of large amounts of missing data (i.e., more than 15%), multiple imputation analyses will be explored. We will examine rates of missing data for all variables and determine whether the rates vary by participant characteristics, HV program location, or intervention arm. These summarizations will inform potential biases resulting from missing data. The mixed effects models planned for analysis are generally robust for unbalanced data across study time points. We plan to apply multiple imputation in order to account for missing data; we will impute at least five datasets to generate an estimated average intervention effect. These analyses will again serve as sensitivity analyses to the previously outlined analyses. For participants missing individual items on a particular assessment, we plan to randomly sample from the non-missing empirical distribution for that item. We anticipate less than 5% of participants that would require this imputation of individual items. Again, in the event of large amounts of missing individual items, we will explore multiple imputation methods.

Power and Sample Size Considerations

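### Missing questionnaire items are filled from the item's overall distribution without using the woman's own answers; this distorts affected women's scores and MDE status, although the primary contrast barely moves at the expected rate

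*SAP*

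**What the plan says.** The item rule is in the SAP under Analytic Dataset. For participants missing individual items on an assessment, "we plan to randomly sample from the non-missing empirical distribution for that item". No stratification of the donors by arm, visit or severity is given, and the woman's answered items play no stated part. The rule is not tied to one instrument, so it covers both the QIDS-SR16 and the Maternal Mood Screener that defines MDE.

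The SAP limits the expected extent: "We anticipate less than 5% of participants that would require this imputation of individual items". It adds a fallback: "in the event of large amounts of missing individual items, we will explore multiple imputation methods". That sentence has no threshold. For missing data in general one is given: "in the event of large amounts of missing data (i.e., more than 15%), multiple imputation analyses will be explored". Of the multiple imputation with at least five datasets, the SAP says "These analyses will again serve as sensitivity analyses to the previously outlined analyses".

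Under Study Outcomes the SAP says of the validated scales: "The scoring instructions will be followed and analyses will proceed on the final, scored variables". The MDE definition there needs five or more symptoms, at least one of the first two, and a yes to a single interference question. The protocol (Process to Document Consent) lets women skip any question, so some item gaps are to be expected.

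**The concern.** A woman's answered items are the best available predictors of the one she skipped, and a draw from the item's marginal distribution discards them. Whatever her severity, the imputed value has the overall item mean as its expectation. Severe scores are pulled down and low scores are pulled up.

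MDE status is more exposed because it is a threshold rule: one drawn answer can settle it. The result feeds three places in the SAP: a secondary outcome, an adjustment covariate in the primary model (baseline at-risk status) and the secondary analysis of women at risk at baseline.

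If the draws also pool the arms, imputed items carry no arm difference, so contrasts shrink towards zero. For the superiority comparison that is conservative. For non-inferiority it is the favourable direction.

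**Working it through.** **The plan's own figures.** The SAP gives no figure for the effect of item imputation. Its power assumptions supply the standard error used below, so I checked those first. A noncentral t test with design effect 1 + (m − 1) × ICC, 2(k − 1) degrees of freedom, SD 6, difference 2 and two-sided alpha 0.017 returns all 12 entries of SAP Table 1. At 16 sites per arm, 23 women per site and ICC 0.01, non-inferiority power is 93.3% with alpha 0.05/3 (SAP: over 90%). The standard error is 6 × √[2 × (1 + 22 × 0.01) / (16 × 23)] = 0.489.

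**Effect on an affected woman's QIDS score.** All of this rests on an assumed model: nine equally weighted parts scored 0-3, which fits a total that is "This is a continuous measure ranging from zero to 27 points, where higher scores signify increased depressive symptoms"; one factor with loadings 0.60-0.75; items missing completely at random. With one part missing, a marginal draw shifts the total as follows:

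| True score | Mean shift |
|---|---|
| 0-5 | +0.5 to +0.7 |
| 16-20 | −1.0 to −1.2 |
| 21-27 | −1.6 to −1.8 |

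For a common item at loading 0.6, the top-decile bias is −1.19 with the marginal draw and −0.28 with a draw conditional on her other items.

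**Is proration the obvious replacement?** Not for rare items. The protocol's safety monitoring section expects under 1% of women to choose the most severe suicidality response, so item means differ. With one rare part (any endorsement by 10%, assumed; loading 0.6), proration has mean bias +0.81 and RMSE 1.05. The marginal draw has mean bias 0.00 and RMSE 0.66. In the top decile the biases are about +1.57 and −0.53.

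**MDE status.** If only the interference answer is missing and it is drawn independently, a true case is kept with probability equal to the donors' yes-rate. Under assumed loadings of 0.60-0.75 and MDE prevalence of 15-20%, that rate is about 29-39%, so 61-72% of such cases are lost. A drawn symptom 1 or 2 loses 15-20% of true cases, and one random symptom 8-12%. Non-cases become cases in 0.6-5.7%. The net effect is under-classification.

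How many women is that? The SAP's power section implies 38 × 23 = 874 analysable women, and 5% of these is about 44. Suppose each misses exactly one of ten screener items, spread evenly (nine symptoms plus interference; the SAP does not state the symptom total). About 4.4 would miss the interference item. At 15-20% MDE, the two incidence figures in the protocol's power analysis, that is 0.7 to 0.9 of a true case. Even if all 5% missed the interference item, overall MDE prevalence would change by at most about 0.5 percentage points.

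**Arm contrast, if donors are pooled over arms.** With a share p of women imputed and k of nine parts missing for each, the difference D shrinks by D × p × k/9. One-sided error at the non-inferiority margin is Φ(−1.96 + shrinkage/0.489).

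| p | k | Shrinkage, D = 5 | Shrinkage, D = 2 | One-sided NI error (nominal 0.025) |
|---|---|---|---|---|
| 0.05 | 1 | 0.028 | 0.011 | 0.026 |
| 0.05 | 3 | 0.083 | 0.033 | 0.029 |
| 0.15 | 3 | 0.25 | 0.10 | 0.040 |

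First row: 5 × 0.05 × 1/9 = 0.028, and 2 × 0.05 × 1/9 = 0.011.

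**The case against.** The strongest reply is about size. The SAP expects under 5% of women to need the rule, and at that ceiling no trial conclusion would plausibly change. This stands, and it sets the weight of the point.

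The SAP also promises to look at multiple imputation if many items are missing, and to examine missingness by arm and participant characteristics. That is a genuine safeguard, but a partial one: "large" has no item-level threshold, and nothing says the planned multiple imputation would redo the item draws.

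A reader might infer several stronger things that the documents do not support:

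- **That a single draw is taken from all women in all arms.** The SAP states neither the number of draws nor the donor pool. An arm-specific pool would remove the shrinkage described above.
- **That the rule contradicts the commitment to follow scoring instructions.** It can be read as covering only what those instructions leave open. Whether they contain missing-item rules cannot be settled from the documents.
- **That most MDE cases with a missing interference answer would certainly be lost.** The percentage restates an assumed yes-rate. If only women reporting symptoms answer that question, the donors are symptomatic and more cases are kept. The documents do not say.

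It is also fair to say that the SAP's rule beats proration for a rarely endorsed item.

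**Conclusion.** The point holds as a cheap improvement to the imputation rule. Followed as written, the rule gives worse scores and less reliable MDE status for affected women than a draw that uses their own answers. The direction follows from the rule itself. The sizes (about 1 point per common missing item in the top decile, and the MDE percentages) depend on the assumed one-factor model, equal weighting of parts and items missing completely at random.

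The documents do not support reading this as a threat to the superiority or non-inferiority conclusion. At under 5% of women with one to three parts missing, the contrast moves by about 0.01 to 0.08 points, and only if donors are pooled over arms. It would begin to matter if item gaps were well above that rate, or concentrated among severely depressed women or in deciding items.

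**What to change.** Amend the item-level paragraph of the Analytic Dataset section:

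1. Where an instrument has its own missing-item rule, apply it, and say that it takes precedence.
2. Otherwise replace the marginal draw with item-level imputation conditional on the woman's other items, arm and visit, carried out within the multiple imputation so that its uncertainty is reflected.
3. Do not use simple proration as the general fallback, because it is biased upwards for rarely endorsed items such as suicidality.
4. Treat MDE status as missing, and impute it conditionally, only when the unanswered items could change the classification. Where the answered items already settle it, use them.
5. Define what counts as a large amount of item-level missingness.

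The cost is SAP wording and a little more programming. The SAP's Technical Details section already provides for documented changes to the analysis.

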4. Of those that meet acceptable levels of imbalance, we randomly select one allocation for use in the current study.

We chose the p-value corresponding to the Kruskal-Wallis test (nonparametric version of an Analysis of Variance [ANOVA]) as our criterion for 'balance' in step #3 above. If the p-value for each of the three variables is larger than 0.30 for a given simulated allocation scheme, that particular allocation is deemed 'acceptable'. This criterion is adapted from the 'Minimal Sufficient Balance' principle from Zhao et al. [3] in the individual sequential randomization literature.

In the current study, randomization occurred in three waves for logistical purposes. The first included 14 sites (2 C:6 HV:6 MH); the second included 19 sites (4 C:7 MH:8 HV); allocation ratio was slightly off in this wave to account for dropout sites); and the third wave included 12 sites (1 C:6 MH:5 HV). Thus, we randomized a total of 45 sites in three waves; randomization of 42 sites was the study goal, reflected in our approved research plan. However, to account for site dropping out in the meantime, we adapted the algorithm to increase the number of sites randomized and also to allow for slightly discrepant allocation ratios than the planned 1:3:3 within each wave.

After randomization, eight programs dropped out, thereby yielding a total of 37 study sites contributing data for analyses. Data collected from all study participants will be used in the analysis. Among the 37 active study sites, 16 HV programs received the MB intervention delivered by mental health professionals, 15 received MB intervention delivered by HV paraprofessionals, and six programs serve as control sites. As an aside, 29 intervention sites ended up implementing at least one cohort (15 MH, 14 HV).

Statistical Methods

Descriptive statistics will summarize baseline characteristics (both site-level and participant-level) overall and by arm. As appropriate, mean \pm standard deviation (or median [inner quartile range]) will be used in cases of skewed or non-normal empirical distributions) and frequency (proportions) will summarize continuous and categorical data, respectively. Analyses will employ normal theory methodology as appropriate, and in cases of violations of assumptions, transformations and/or nonparametric analyses may be utilized.

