We initially planned to conservatively enroll 42 sites (six controls, 18 HV-led, 18 MH-led) with a target enrollment of 40 participants per site (1680 total participants). As in any cluster-randomized trial, power and sample size considerations depend heavily on intra-cluster correlation coefficient (ICC) estimates. In general, it is recommended that these calculations account for anticipated ICC as failure to do so in the design phase and lead to an increase in type II error (i.e., result in underpowered studies) [4, 5]. Without previous knowledge of ICC(s) in this population with respect to our primary outcome, we explored a range of ICCs (0.001 to 0.05). Power calculations assume a standard deviation in primary outcome of approximately six points (on the QIDS-SR16), with a meaningful difference corresponding to five points on average across arms. Thus, for the superiority aim, we calculated power based on the average ability to detect at least a five-point mean difference between control sites and HV-led sites. Power calculations assumed a $5\%/3 = 1.7\%$ level of significance in order to account for three pairwise comparisons. This is an approach that we deem conservative as this mirrors the Bonferroni correction for multiple hypothesis tests.

We have 38 active sites: six control, 16 paraprofessional home visitor-led sites, and 16 MHP-led sites. We plan to recruit an average of 27 participants per site, allowing for up to 15% attrition (i.e., 23 participants on average for analyses). These assumptions allow for more than 95% power to detect a mean difference of five points in QIDS-SR16 across arms for an ICC of 0.01. Even if one of the six sites drops out, and if ICC is as large as 0.05 (which we deem unlikely), we still anticipate over 85% power for analyses addressing the efficacy aim (Aim #1).

Power for the NI aim will require ability to detect a smaller (margin of NI of two points) mean difference across arms. We anticipate over 90% power to detect a margin of NI of two points on the QIDS-SR16 scale if we assume an ICC of 0.01 and 16 sites in each of the intervention arms with 23 participants for analyses, on average, per site. This allows for up to 15% attrition overall. We anticipate some sites to be over/underperforming and thus unequal representation per site is inevitable. Our hope is that the precautions taken with respect to the randomization algorithm that

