attempts to control imbalance in yearly volume and population density will offset biases created by over/underrepresentation for participants at specific sites. While we do not anticipate ICC to be larger than 0.01 [4], we present the required sample size per site in Table 1 below in order to ensure 90% power under the same assumptions for all scenarios explored. We also present sample size requirements in the event that one of the active sites drops out in each of the intervention arms (i.e., 15 sites per arm). Notice that if ICC is larger than 0.02 (which we are not anticipating, although it remains possible), our projected sample size does not allow for 90% power in this case. Since these assumptions are all rather conservative, we argue adequate power for detection of both superiority and non-inferiority. Power calculations for assessment of heterogeneity of intervention effects depending on participant characteristics (Aim #3) require even more assumptions for which we have little information. Thus, we do not necessarily anticipate power to detect specific effects within subgroups or power to detect interaction effects, but we plan to use the analyses outlined here to explore these effects.

Table 1. Required Sample Size for 90% Power in Non-inferiority Aim

ICC	N HV sites	N MH Sites	N per site for analyses	N recruited per site (allowing for 15% attrition)
0.001	16	16	17	20
0.01			20	23
0.02			25	29
0.03			33	39
0.04			49	58
0.05			97	114
0.001	15	15	19	22
0.01			22	26
0.02			28	33
0.03			38	45
0.04			62	73
0.05			168	198

Technical Details

The SAP is subject to version control and we anticipate modifications to analytic plans be documented herein. As in any study, the analytic plan may change due to assumption violations, logistical issues, and/or unexpected empirical distributions of study outcomes. In these cases, the statistical analysis plan will be updated accordingly. All analyses will be performed via SAS version 9.4 or higher (The SAS Institute; Cary, NC) or R version 3.4.1 or higher (The R Foundation for Statistical Computing platform). Example t table shells are included below. Note that these are not binding and may be adapted as needed as formatting and style may be dictated by mode of dissemination or specific target journal(s) for results dissemination.

Timeline for Analyses

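### The SAP's stated ICC limit for 90% non-inferiority power (0.02) and its HV site count (16) do not match its own Table 1 and randomization section; the power claim at ICC 0.01 stands

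*SAP*

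**What the plan says.** Three statements in the SAP's Power and Sample Size Considerations matter here.

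- Projected size: "We plan to recruit an average of 27 participants per site, allowing for up to 15% attrition (i.e., 23 participants on average for analyses").
- Sites: "We have 38 active sites: six control, 16 paraprofessional home visitor-led sites, and 16 MHP-led sites".
- Non-inferiority power: "We anticipate over 90% power to detect a margin of NI of two points on the QIDS-SR16 scale", given an ICC of 0.01, 16 sites in each intervention arm and 23 analysed per site.

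On larger ICCs, the text above Table 1 (required sample size) says: "Notice that if ICC is larger than 0.02 (which we are not anticipating, although it remains possible), our projected sample size does not allow" 90% power. At ICC 0.02 the table itself lists 25 analysed and 29 recruited per site with 16 sites per arm, and 28 and 33 with 15 per arm.

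Randomization Methods gives a different site count: "After randomization, eight programs dropped out, thereby yielding a total of 37 study sites contributing data for analyses". Of these, "16 HV programs received the MB intervention delivered by mental health professionals, 15 received MB intervention delivered by HV paraprofessionals", and six are controls.

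**The concern.** The sentence on the ICC is not literally false, because every table row above 0.02 does need more than 23 analysed per site. But it sets the boundary at 0.02, and so implies that 0.02 itself keeps 90% power. The table below it shows that 0.02 already fails with the projected numbers: 23 is less than 25 (or 28) analysed, and 27 is less than 29 (or 33) recruited.

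Separately, the power section counts one more HV site than the randomization section, and the SAP does not say which count is current. The HV arm enters both the superiority and the non-inferiority comparison. The table has no block for 15 HV and 16 MH sites, the split that the randomization section reports.

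The limit matters because the SAP chose its ICC range "Without previous knowledge of ICC(s) in this population with respect to our primary outcome". The sentence is its only statement in prose of how much clustering the non-inferiority comparison can absorb at 90% power, and a claim of adequate power for both aims follows shortly after.

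**Working it through.** **Inputs, all from the SAP's power section unless noted**

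- SD 6: "Power calculations assume a standard deviation in primary outcome of approximately six points (on the QIDS-SR16").
- Margin 2 points. True difference 0 (assumed).
- Significance level 5%/3, given as 1.7%. Sidedness is not stated; two-sided 0.017 is what reproduces the table.
- m = 23 analysed per site (27 × 0.85 = 22.95).
- Sites per arm: 16 and 16 (power section), 15 HV and 16 MH (Randomization Methods), 15 and 15 (second block of the table).
- Equal cluster sizes and no covariate adjustment.

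**Method**

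SE = 6 × √{[1 + (m − 1) × ICC] × [1/(k₁m) + 1/(k₂m)]}. Power comes from the noncentral t distribution with k₁ + k₂ − 2 degrees of freedom and noncentrality 2/SE.

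**Step 1: reproduce the table**

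The smallest m with power of at least 90% is:

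| ICC | 0.001 | 0.01 | 0.02 | 0.03 | 0.04 | 0.05 |
|---|---|---|---|---|---|---|
| 16 + 16 | 17 | 20 | 25 | 33 | 49 | 97 |
| 15 + 15 | 19 | 22 | 28 | 38 | 62 | 168 |

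All 12 analysed-per-site entries match the SAP exactly. A normal approximation at the same level does not (16, 18, 22, 27, 37, 60 for 16 + 16). Nor does a one-sided 0.017 level or a 0.05 level.

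**Step 2: power with the projected 23 per site**

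Worked case, 16 + 16 sites, ICC 0.02:

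- Design effect: 1 + 22 × 0.02 = 1.44.
- SE: 6 × √[1.44 × 2/(16 × 23)] = 0.531.
- Noncentrality: 2/0.531 = 3.77.
- Critical t on 30 df: 2.527.
- Power: 88.5%.

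| Sites (HV + MH) | ICC 0.01 | ICC 0.02 | ICC 0.03 | ICC at which power is 90% |
|---|---|---|---|---|
| 16 + 16 | 93.4% | 88.5% | 83.0% | 0.017 |
| 15 + 16 | 92.5% | 87.2% | 81.4% | 0.015 |
| 15 + 15 | 91.5% | 85.8% | 79.9% | 0.013 |

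At ICC 0.02 the shortfall from 90% is 1.5 points with 16 + 16 sites and 2.8 points with 15 + 16. At ICC 0.01 power exceeds 90% in every row.

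**Step 3: what 15 HV and 16 MH sites would need**

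For ICC 0.001, 0.01, 0.02, 0.03, 0.04 and 0.05, the analysed number per site is 18, 21, 26, 36, 55 and 124. At ICC 0.02, 26/0.85 = 30.6, so 31 recruited, against 23 analysed and 27 recruited as projected.

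**Step 4: the site counts**

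Summing the three randomization waves:

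- control: 2 + 4 + 1 = 7
- HV: 6 + 8 + 5 = 19
- MH: 6 + 7 + 6 = 19
- total: 45

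Then 45 − 8 dropouts = 37, and 16 MH + 15 HV + 6 control = 37. The randomization section therefore agrees with itself. The power section's 6 + 16 + 16 = 38 exceeds it by one, and the extra site is in the HV arm.

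**The case against.** The arithmetic is not in dispute. The case on the other side has four parts.

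1. **The sentence is true as written, and the shortfall is visible.** The only affirmative power claim is at ICC 0.01, and a reader can compare 23 with 25 unaided. This is correct, and it is why the point is minor. The prose still places the boundary where the table shows it has already been crossed.

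2. **The lower HV count is already allowed for.** The table's 15 + 15 block is more pessimistic than 15 + 16 and needs 22 at ICC 0.01, within the projected 23. The two counts may also date from different times. The first part stands for the claim at ICC 0.01. The second is conjecture, since the SAP dates neither count.

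3. **The planned analysis differs from the table's method, so a limit of 0.015 or 0.017 looks too exact.**
   - With a Tukey critical value (assuming df = sites minus 3), power at ICC 0.02 is 90.05% for 16 + 16 and 88.9% for 15 + 16.
   - Adjusting for baseline score would help. At an assumed baseline–outcome correlation of 0.3, with the ICC held fixed, power is 91.5% and 90.4%; at 0.2 it is 89.9% and 88.6%.
   - Unequal site sizes, which the SAP expects, would hurt. At an assumed coefficient of variation of 0.5, the 15 + 16 limit falls to about 0.012.

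   These caveats are fair, but they pull in both directions. The correlation and the coefficient of variation are not given in the documents. The sentence summarises a table built on none of these refinements, and it should agree with that table.

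4. **The endorsement at ICC 0.01 has conditions of its own.** With 15 + 16 sites and an assumed coefficient of variation of 0.7, unadjusted power is 89.9%. The endorsement is therefore on the table's basis of equal site sizes. On that basis it holds even for the 14 HV and 15 MH sites that ran at least one cohort (90.3%).

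**Conclusion.** The concern holds, at minor severity. On the SAP's own basis (SD 6, margin 2, two-sided 0.017, equal site sizes, no covariate adjustment), 23 analysed per site does not give 90% non-inferiority power at ICC 0.02 under any of the site counts considered. The true limit is an ICC of about 0.017 if there are 16 HV sites and about 0.015 if there are 15. The two site counts contradict each other, and only the count of 37 follows from the randomization and dropout figures that the SAP reports. No non-inferiority conclusion at the planning ICC of 0.01 is affected.

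**What to change.** Keep the statement of over 90% power at ICC 0.01. Then:

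1. Reconcile the site counts in Randomization Methods and Power and Sample Size Considerations, and say which is current. If the randomization section is current, this is 37 sites with 15 in the HV arm.
2. Restate the limit, for example: with 23 analysed per site and under the table's assumptions, 90% power is not available once the ICC exceeds about 0.015 (about 87% at 0.02 and 81% at 0.03). If 16 + 16 is the current count, the figures are about 0.017, 88% and 83%.
3. Optionally, add a block for 15 HV and 16 MH sites to the table, using the numbers in Step 3.

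The cost is SAP wording only. Recruitment, analysis, margin and decision rule do not change.
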